5.5.1 Standard Risk Minimization Strategies

Standard risk minimization strategies include:

- I. Cardiologists with training and education in pediatric cardiology and with expertise in using the Amplatzer Piccolo Occluder device to close PDAs
- II. Prior experience with transcatheter closure procedures using similar devices with a minimum of 10 cases in subjects < 2 kg.
- III. Institutions will have the necessary infrastructure to support studyprocedures:

Confidential

- a. Cardiac catheterization lab or NICU bedside capability to perform intra-procedural echocardiography and fluoroscopy
- b. Anesthesiology support, as needed
- c. Catheterization laboratory, operating room, post anesthesia recovery, intensive care and step down unit spaces to accommodate cases with and without complications
- d. On-site emergency cardiac surgery services
- e. Adequate monitoring for each clinical investigation site
- f. Conducting the clinical investigation in accordance with the study, all applicable laws and regulations and any conditions of approval imposed by the appropriate IRB or applicable regulatory authorities where the clinical investigation is performed
- g. Preparation of the device and implant procedure in accordance with the device IFUs
- h. Training of Investigators both on the study protocol and implant procedure
- i. All site staff will participate and complete a raining module
- j. Implanting physicians with no prior successful transcatheter PDA closure experience in small infants (<2 kg) will receive proctoring for a minimum on one case.
- k. Assessment of continuing safety of subjects in the clinical investigation by an independent Clinical Events Committee (CEC).
- 1. Physicians are required to follow The American Heart Association Recommendations for endocarditis prophylaxis during the clinical study.
- m. Sites should follow patients per their standard of care for any reported adverse events.

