A subject will be considered 'Lost to Follow-up' after two missed scheduled visits within the 6month window, a minimum of two unsuccessful phone calls from investigational site personnel to the subject. These two phone calls must be documented in the subject's research records. If the subject is deemed lost to follow-up, a certified letter will be sent to the subject's last known address or to the subject's general practitioner (GP). A copy of the letter must be maintained in the subject's research records.

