6.1 Subject Death

Subject deaths will be documented and reported to the CCISC PDA Module PI as soon as possible (but no later than 3 business days) after becoming aware of the event via the applicable case report form (CRF) within the PDA module. In the event an autopsy is performed whenever possible data on the histopathology of the Amplatzer Piccolo Occluder device should be submitted within the case report form including any photographs of the gross and microscopic findings.

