7.1 Primary Safety Endpoint

The primary safety endpoint is the rate of major adverse events through up to six-months after an attempted device implant (refer to **Appendix A** for definition).

The proportion of subjects experiencing a major AE through up to six-months will be estimated. The 95% confidence interval for the percent of major AE will be calculated using the exact binomial method. The numerator for the event rate is the number of subjects who experienced an event through up to six-months. The denominator is the number of subjects in the analysis population (As detailed in Section 7.4). The primary safety endpoint rate will be descriptively compared with the rate reported in the Amplatzer Piccolo Occluder IDE and Continued Access Protocol studies. The overall estimated rate for major complications based on published literature ranges between 4.0 to 10.0%.

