7.4 Analysis Population

The analysis of the primary and secondary endpoints will include all subjects who achieve a successful implant, which is defined as leaving the catheterization lab with a device implanted in the PDA. If a subject has multiple devices attempted during the same procedure, but leaves procedure with at least one device within the PDA the procedure is considered successful. Subjects without an implanted device in the PDA will be excluded. Additionally, subjects who had no follow- up visits up to the six-months +/- one-month window, or lost to follow-up will be excluded.

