8.2 Safety reporting

Safety surveillance within this study (and the safety reporting performed by the investigator), starts as soon as the subject is referred for PDA closure. The safety surveillance and the safety reporting will continue until the follow-up visit has been performed, the subject is deceased, the subject/investigator concludes his/her participation into the clinical study or the subject is deemed lost to follow-up. All adverse event data required to be reported will be collected throughout the clinical study and will be reported to the CCISC PDA Module PI.

For the purposes of this clinical study the following events will be reported (see **Appendix A** for definitions):

- a. Unanticipated adverse device effects
- b. All adverse events viewed/interpreted by investigator to be potentially related to either i) the implant procedure or ii) the device regardless of seriousness

Note – If relatedness is unknown or cannot be determined, then the event must be reported.

Note – if a procedure is abandoned and surgical ligation is used to close the PDA, adverse events associated with the surgical ligation will not be reported.

Records relating to the subject's subsequent medical course must be maintained and submitted (as applicable) to the CCISC PDA Module PI until the event has subsided or, in case of permanent impairment, until the event stabilizes and the overall clinical outcome has been ascertained. Adverse events will be monitored until they are adequately resolved. The status of the subject's condition should be documented at periodic intervals.

Subject deaths will be documented and reported to the CCISC PDA Module PI as soon as possible (but no later than 3 business days) after becoming aware of the event via the applicable CRF. If an unanticipated adverse device effect occurs, the investigator must notify the CCISC PDA Module PI and the IRB immediately, but no later than 10 working days of the investigator's knowledge of the event, as required by 21 CFR §812.150. The CCISC will take any steps necessary to investigate the event, and, as appropriate, will be responsible for notifying FDA and all other participating IRBs and investigators.

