The adverse event is related to the study device/procedure – i.e. an event that follows a reasonable temporal sequence from administration of the study intervention, follows a known or expected response pattern to the suspected intervention, that is confirmed by improvement on stopping and reappearance of the event on repeated exposure and that could not be reasonably explained by the known characteristics of the subject's clinical state.

In summary, the AE is related to any study device or procedure if the event satisfies all of following criteria:

- a. Has a reasonable temporal relationship to intervention (e.g. device implant)
- b. Could not readily have been produced or explained by the subject's clinical state or have been due to environmental or other interventions
- c. Follows a known pattern of response to intervention
- d. Disappears or decreases with reduction in dose or cessation of intervention and recurs with re-exposure

MajorComplication

Major complications are defined as device or procedure-related adverse events resulting in any of the following:

- a. Death
- b. Life-threatening adverse event,
- c. Persistent or significant disability/incapacity, and/or
- d. A major open surgical intervention which is performed by a surgeon under general anesthesia

Examples of Major Complications:

- a. Device or procedure related events leading to death
- b. Cardiac perforation requiring percutaneous (e.g., pericardiocentesis) or open surgical intervention
- c. Cardiac tamponade
- d. Embolization requiring open surgical procedure (e.g., open heart surgery or femoral vessel cut down procedure) to retrieve the device
- e. Persistent hemodynamic instability requiring emergency cardioversion/defibrillation therapy or emergency blood transfusion and/or institution of inotropic therapy
- f. Excessive blood loss or hemolysis requiring transfusion > 20 cc/kg
- g. Persistent or worsening respiratory instability
- h. Cerebral or pulmonary embolism
- i. Persistent cardiac arrhythmia requiring a pacemaker
- j. Arteriovenous fistula requiring open surgical intervention
- k. False aneurysm of the femoral artery requiring surgical intervention
- l. Femoral vessel thrombophlebitis treated with intravenous antibiotics
- m. Infection of the device (bacterial endocarditis)

Minor Complication

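### The follow-up exclusion in Protocol Section 7.4 can remove major events already on record from the primary safety rate

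*Protocol*

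**What the plan says.** Section 7.4 sets a single population for the primary and secondary endpoints: subjects who leave the catheterization laboratory with a device in the duct. It then narrows that group: "subjects who had no follow- up visits up to the six-months +/- one-month window, or lost to follow-up will be excluded". No exception is stated.

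Section 7.1 defines the primary safety endpoint as major adverse events from the attempted implant to six months. On the count it says: "The numerator for the event rate is the number of subjects who experienced an event through up to six-months". The denominator is the Section 7.4 population, the interval is exact binomial at 95%, and the published range for major complications is given as 4.0 to 10.0%. On use of the result: "The primary safety endpoint rate will be descriptively compared with the rate reported in the Amplatzer Piccolo Occluder IDE and Continued Access Protocol studies".

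Three other places bear on who is excluded:

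- Section 6 (Study Completion) treats a subject as lost "after two missed scheduled visits within the 6month window, a minimum of two unsuccessful phone calls". The definition turns on attendance and contact only.
- Appendix A lists "Device or procedure related events leading to death" among the major complications.
- Section 8.2 names death and loss to follow-up as separate ends of surveillance, so a death is not in itself a loss.

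Sections 7.5d to 7.5f report complications, deaths and losses descriptively. Sections 7.5d and 7.5e name no population.

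**The concern.** Excluding subjects without follow-up is understandable for the effectiveness endpoint, which Section 7.2 bases on an echocardiogram at six months. It does not suit a cumulative safety endpoint. Once a major event is recorded, later absence cannot change the subject's status, so nothing is missing that would justify exclusion. Section 7.1 counts everyone who had an event, while Section 7.4 removes some of those same people.

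With no formal test, the estimate and its interval are the primary safety result, and this is the rate to be set beside the IDE and Continued Access studies. It may leave out outcomes the registry already holds, including related deaths.

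**Working it through.** **Which recorded outcomes can leave the rate**

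1. *Event, then loss.* An infant has a major event recorded at the procedure or the 48-hour visit, misses the 1-month and 6-month visits and cannot be reached by two calls. Section 6 makes the infant lost, and Section 7.4 excludes the infant however its visit clause is read.
2. *Related death.* Here the visit clause of Section 7.4 matters. If it means no visit at any time, only a death before the 48-hour visit is at risk, and even that can be argued because Appendix E collects death data in that column. If it means no visit inside the six-month window, every related death before the window is removed.

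**Illustrating the size**

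The protocol states no hypothesis, power or derivation of the sample size, so there is no figure of its own to reproduce. Inputs:

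- From the protocol: 500 subjects (Sections 2 and 13), major complications of 4.0 to 10.0% and the exact binomial interval (Section 7.1).
- Assumed: all 500 are implanted; *m* = 25 or 50 are excluded for follow-up; *k* of the *E* recorded events are among them.

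Formulas:

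- Section 7.4 as written: (*E* − *k*)/(500 − *m*)
- (a) All implanted: *E*/500
- (b) Recorded events kept, event-free lost subjects dropped: *E*/(500 − *m* + *k*)

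For *E* = 20 (4%), (a) is 20/500 = 4.00% (95% CI 2.46–6.11). For *E* = 50 (10%), (a) is 50/500 = 10.00% (7.51–12.97). The other two rates are:

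| *E* | *m* | *k* | Section 7.4 as written | (b) events kept |
|---|---|---|---|---|
| 20 | 50 | 0 | 20/450 = 4.44% (2.74–6.78) | 20/450 = 4.44% (2.74–6.78) |
| 20 | 50 | 2 | 18/450 = 4.00% (2.39–6.25) | 20/452 = 4.42% (2.72–6.75) |
| 20 | 50 | 5 | 15/450 = 3.33% (1.88–5.44) | 20/455 = 4.40% (2.71–6.71) |
| 20 | 25 | 0 | 20/475 = 4.21% (2.59–6.43) | 20/475 = 4.21% (2.59–6.43) |
| 20 | 25 | 1 | 19/475 = 4.00% (2.43–6.18) | 20/476 = 4.20% (2.59–6.41) |
| 20 | 25 | 2 | 18/475 = 3.79% (2.26–5.92) | 20/477 = 4.19% (2.58–6.40) |
| 20 | 25 | 5 | 15/475 = 3.16% (1.78–5.16) | 20/480 = 4.17% (2.56–6.36) |
| 50 | 50 | 0 | 50/450 = 11.11% (8.36–14.39) | 50/450 = 11.11% (8.36–14.39) |
| 50 | 50 | 5 | 45/450 = 10.00% (7.39–13.15) | 50/455 = 10.99% (8.27–14.23) |
| 50 | 50 | 10 | 40/450 = 8.89% (6.43–11.91) | 50/460 = 10.87% (8.18–14.08) |

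The written rule equals (a) exactly when *k*/*m* = *E*/500, that is, when events are as frequent among the excluded as overall. It falls below (a) when they are more frequent and rises above it when they are less frequent.

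Rate (a) is the lowest rate the recorded events allow, because it counts every lost, event-free subject as event-free throughout. At 3.33%, 3.16% or 8.89% the written rule reports less than that floor.

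**The case against.** *The routes are narrow.* The Section 6 wording on missed visits could refer to the six-month visit window rather than the six-month period, in which case missing the 1-month and 6-month visits would not make a subject lost. But Appendix E schedules only one visit in that window, so on that reading nobody could miss two, although Sections 7.4 and 7.5f plainly expect losses. Whichever visits count, loss is defined without regard to recorded events. For deaths, no visit at any time is arguably the more natural reading of Section 7.4, and the reach is then small. That stands.

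*Subjects with events are followed closely.* Section 8.2 says "Adverse events will be monitored until they are adequately resolved" and Section 5.5.1 says "Sites should follow patients per their standard of care for any reported adverse events". This makes loss after an event less likely, but it does not return a lost subject to the Section 7.4 population.

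*The events are reported anyway.* Section 7.5d gives the percentage of major complications from the implant procedure onward with no stated follow-up exclusion, and Section 7.5e gives deaths. A reader would probably see the dropped events there. That limits the harm but leaves the primary rate uncorrected.

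*The figures are soft and the remedy is not neutral.* Five of 20 events among 50 excluded is 10%, or 2.5 times the overall 4%, and nothing in the protocol supports that ratio. At *k* = 0 the shift from 4.00% to 4.44% is ordinary attrition, not dropped events. Every 4% result under the written rule lies within the 2.46–6.11% interval of 20/500. Rate (b) makes inclusion depend on the outcome and tilts upward: with *m* = 50 and *k* = 2 it moves 4.00% to 4.42%. All of this is true, and it is why (a) and (b) should be shown together.

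*An analysis plan may deal with it.* It may, but the protocol has not left the matter open: it states the exclusion and applies it to safety.

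**Conclusion.** The concern holds. It rests on the text: an unqualified follow-up exclusion is applied to a cumulative safety endpoint, so a settled outcome can be dropped. The route through loss after a recorded event does not depend on how the visit clause is read; the reach for related deaths does.

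The size and direction cannot be derived from the protocol, which gives no loss rate. Under the assumptions shown, the written rule gives 3.16% to 4.44% where the all-implanted rate is 4.00%, and 8.89% to 11.11% where it is 10.00%. No decision threshold is affected, because Section 7.6 states that there is no formal hypothesis and the comparison is descriptive. The point should be fixed, but it does not threaten the study.

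**What to change.** In Section 7.4:

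- State that, for the primary safety endpoint, every successfully implanted subject with a recorded major event through six months, including a device- or procedure-related death, stays in numerator and denominator whatever the later follow-up.
- Say whether the visit clause means no follow-up visit at any time or none within the six-month window.
- Report two rates with the exact binomial interval already planned: (a) all implanted subjects, and (b) recorded events kept with event-free lost subjects dropped. Note beside them that (a) is the lower bound and (b) tilts upward.

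The cost is one or two sentences and one extra rate with its interval, with no new data collection. The reported rate may move either way. With 20 events and 50 excluded, if none of the events is among the excluded, 4.44% stays 4.44% under (b) and becomes 4.00% under (a). If five are, 3.33% becomes 4.40% under (b) and 4.00% under (a).

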7.5 Other Endpoints

The following endpoints will be summarized using descriptive statistics.

a. **Implant success:** The frequency and percentage of implant success (defined in Section 7.4) will be reported. This analysis will include all subjects entered in the PDA module.

- b. **PDA shunt status at follow-up visit**: The frequency and percentage of PDA shunt status at the 6 month follow-up visit, as assessed by the TEE, will be reported. Shunt sizes categories are: Grade 0/1, 2, and Grade 3/4. This analysis will include subjects who achieve a successful implant.
- c. **Obstruction measurements at follow-up visit**: The frequency and percentage of significant obstruction of the left pulmonary artery and the frequency and percentage of significant aortic obstruction (defined in Section 7.3) at the 6 month follow-up visit will be reported. Both analyses will include subjects who achieve a successful implant.
- d. **Major and Minor Complications**: The frequency and percentage of major and minor complications (refer to **Appendix A** for definition) from the time of the implant procedure will be reported.
- e. **Death**: The frequency and percentage of death will be reported.
- f. **Additional data**: Demographics and baseline characteristics, procedure information, left ventricular function and dimensions, pulmonic and tricuspid regurgitation, adverse events, subjects lost to follow-up will also be summarized.

7.6. Justification of Clinical Study Design

Based on the IMPACT registry, there are over 6000 transcatheter device closures of PDA that occurs in the United States annually. However, there are no comprehensive data collection tools for this procedure. The current databases do not include multiple data points, or follow-up data, or a section for specific adverse events to be documented. Moreover, until now, there has been no approved devices for PDA closure in children < 2kg. This clinical study is the first of its kind to collect data from all transcatheter device closure of PDA in children < 2kg performed at the CCISC participating centers. This study will be limited to children between 700 to 2000 grams who are the most vulnerable population undergoing this procedure. This will allow us to understand the real world experience (efficacy and safety) of using the Amplatzer Piccolo Occluder device in an extremely vulnerable, yet highly underserved population. The study will allow for standardization of this procedure throughout the country for the small children (<2 kg) with a PDA. This is a multicenter, single arm, observational data collection study. This will be a large population study to help analyze outcomes in subjects <2 kg. The trial has two primary endpoints for safety and effectiveness without formal hypothesis. The safety and effectiveness results will be compared with data reported in the Amplatzer Piccolo Occluder IDE and Continued Access Protocolstudies.

8 REQUIREMENTS FOR INVESTIGATOR RECORDS AND REPORTS

8.1 Deviations from Clinical Study Protocol (CSP)

A deviation is defined as an instance(s) of failure to follow, intentionally or unintentionally, the requirements of the CSP. The investigator should not deviate from the CSP. In some cases, failure to comply with the CSP may be considered failure to protect the rights, safety and well-being of subjects; such non-compliance exposes subjects to unreasonable risks. Examples: failure to adhere to the inclusion/exclusion criteria, failure to safeguard protected health information (PHI) failure to perform safety assessments intended to detect adverse events. Investigators should seek to minimize such risks by adhering to the CSP.

If certain assessments such as details of the echocardiogram, RSS, etc., is not performed or completed within the CRF, it may not be considered as a deviation as determined by the National PI. The PI must maintain accurate, complete, and current records, including documents showing the date of and reason for each deviation from the CSP. Relevant information for each deviation will be documented as soon as possible on the applicable CRF within the PDA module. The site will submit the CRF to the CCISC PDA Module PI. The PI is required to adhere to local regulatory requirements for reporting deviations to IRB. An investigator shall notify the CCISC PDA Module PI and the reviewing IRB of any deviation from the investigational plan to protect the life or physical well- being of a subject in an emergency. Such notice shall be given as soon as possible, but in no event later than10 working days after the emergency occurred. The protocol deviation reporting form and a log are provided in Appendix F.

8.2 Safety reporting

Safety surveillance within this study (and the safety reporting performed by the investigator), starts as soon as the subject is referred for PDA closure. The safety surveillance and the safety reporting will continue until the follow-up visit has been performed, the subject is deceased, the subject/investigator concludes his/her participation into the clinical study or the subject is deemed lost to follow-up. All adverse event data required to be reported will be collected throughout the clinical study and will be reported to the CCISC PDA Module PI.

For the purposes of this clinical study the following events will be reported (see **Appendix A** for definitions):

- a. Unanticipated adverse device effects
- b. All adverse events viewed/interpreted by investigator to be potentially related to either i) the implant procedure or ii) the device regardless of seriousness

Note – If relatedness is unknown or cannot be determined, then the event must be reported.

Note – if a procedure is abandoned and surgical ligation is used to close the PDA, adverse events associated with the surgical ligation will not be reported.

Records relating to the subject's subsequent medical course must be maintained and submitted (as applicable) to the CCISC PDA Module PI until the event has subsided or, in case of permanent impairment, until the event stabilizes and the overall clinical outcome has been ascertained. Adverse events will be monitored until they are adequately resolved. The status of the subject's condition should be documented at periodic intervals.

Subject deaths will be documented and reported to the CCISC PDA Module PI as soon as possible (but no later than 3 business days) after becoming aware of the event via the applicable CRF. If an unanticipated adverse device effect occurs, the investigator must notify the CCISC PDA Module PI and the IRB immediately, but no later than 10 working days of the investigator's knowledge of the event, as required by 21 CFR §812.150. The CCISC will take any steps necessary to investigate the event, and, as appropriate, will be responsible for notifying FDA and all other participating IRBs and investigators.

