2.1 Primary Endpoint(s)

Safety Endpoint: Composite rate of major device- or procedure-related adverse events (AE) of interest through 6 months' post-implantation procedure. AEs of interest are broadly categorized as:

- a. Vascular access complications
- **b.** Valvular Injury
- **c.** Device embolization
- d. Pulmonary or aortic vessel stenosis

Access vessel complications include femoral arterial or femoral/jugular venous complications noted during the procedure, immediately after the procedure or delayed (>24 hours). They range from bleeding from access sites, arterial or venous thrombosis with or without the need for treatment to loss of limb secondary to arterial occlusion.

Valvular injury includes damage to the tricuspid valve or other cardiac valve resulting in immediate post-procedural valvular dysfunction.

Device embolization includes malposition of the device either during or after the procedure or delayed (>24 hours). The outcome of device embolization ranges from observation, transcatheter retrieval at time of procedure or at a separate time, surgical retrieval, other end organ damage, tomortality.

Adjacent vessel stenosis includes a narrowing of the aorta or the left pulmonary artery directly as a consequence of device implantation for PDA closure. Vessel stenosis could happen either during or after the procedure or delayed (>24 hours). The outcome of vessel stenosis ranges from no intervention needed to repeated transcatheter and surgical therapies.

For details of each AEs and definitions, refer to **Appendix A**.

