APPENDIX D: ADVERSE EVENT REPORTING FORM

ADVERSE EVENT FORM

Type of adverse event:
Device embolization Access complications Vessel stenosis Valve injury Other
Device embolization:
During the procedure (In the cath lab): Yes 🔜 No 🔜
After the procedure (In recovery): Yes 🔜 No 🔜
Delayed embolization (>24 hours later): Yes 🦲 No 🦲
Embolization site:
Left pulmonary artery Right pulmonary artery
Aorta/systemic artery Right ventricle Other site (Specify)
Outcome of embolization:
Observation only
Successful transcatheter retrieval with PDA occlusion with another device
Successful transcatheter retrieval, PDA not occluded with another device
Successful transcatheter retrieval, PDA surgically ligated
Unsuccessful transcatheter retrieval, PDA occlusion with another device
Unsuccessful transcatheter retrieval, PDA not occluded with another device
Unsuccessful transcatheter retrieval, PDA surgically ligated
Device embolization led to initiation of inotropic suport
Device embolization led to initiation of mechanical circulatory support
Device embolization led to patient mortality
Access complications:
During the procedure (In the cath lab): Yes No
After the procedure (In recovery): Yes No
Delayed access complication (>24 hours later): Yes No
Arterial access complication:
Transient loss of pulse with spontaneous recovery without intervention
Transient loss of pulse with recovery following intervention
Non-occlusive arterial thrombus – No intervention needed/performed
Non-occlusive arterial thrombus – Requiring intervention
Occlusive arterial thrombus – Requiring intervention
Medical Surgical
Loss of limb secondary to vascular access complication
Venous thrombosis – anticoagulation/antiplatelet therapy performed
Venous thrombosis – anticoagulation/antiplatelet therapy not performed

Vessel stenosis:

Noted during the procedure (In the cath lab): Yes Noted after the procedure (In recovery): Yes Delayed finding (>24 hours later): Yes

No	
No	
No	

Left pulmonary artery stenosis:

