No intervention was required Intervention performed during the same catheterization Intervention performed within 24 hours Intervention performed > 24 hours Re-intervention on the left pulmonary artery is unlikely Re-intervention on the left pulmonary artery is likely *Type of intervention for the left pulmonary artery stenosis*: Retrieval of device with no further intervention Retrieval of device with repositioning of the same device Retrieval of device with use of a different device Balloon angioplasty of the left pulmonary artery stenosis Surgical repair

Descending aorta stenosis:

No intervention was required Intervention performed during the same catheterization Intervention performed within 24 hours Intervention performed > 24 hours Re-intervention on the aorta is unlikely Re-intervention on the aorta is likely

Type of intervention for the descending aorta stenosis:

Retrieval of device with no further intervention Retrieval of device with repositioning of the same device Retrieval of device with use of a different device Balloon angioplasty of the descending aorta stenosis Stent implantation for descending aorta stenosis Surgical repair

Valve	e Injury:
	Noted during the procedure (In the cath lab): Yes No
	Noted after the procedure (In recovery): Yes 📃 No 🔜
	Delayed finding (>24 hours later): Yes No
Injure	ed Valve:
	Tricuspid valve
	Pulmonary valve
	Mitral valve
	Aortic valve
Degre	ee of regurgitation:
	Mild
	Moderate
	Severe
Mech	anism of regurgitation:
	Avulsion of chordae
	Avulsion of chordae Central non-coaptation of the valve Valve leaflet injury Injury to valve appulus
	Valve leaflet injury
	Injury to valve annulus
Outco	ome:
	Observation only
	Medical therapy
	Surgical intervention

Other complications: Bleeding into: Pericardium Pleura Peritoneum Retroperitoneum External hemorrhage Vessel perforation Cardiac arrest Arrhythmias including AV heart blocks Stroke Death Infection including suspected endocarditis and sepsis Post PDA ligation syndrome

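### Section 8.2 exempts adverse events of surgical ligation after an abandoned procedure, with no exception for ligation prompted by a device or procedure complication, and so conflicts with its own reporting rules

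*Protocol*

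**What the plan says.** Section 8.2 of the protocol sets the general rule for adverse event reporting: "All adverse events viewed/interpreted by investigator to be potentially related to either i) the implant procedure or ii) the device regardless of seriousness". It adds: "If relatedness is unknown or cannot be determined, then the event must be reported". A second note then says that if "a procedure is abandoned and surgical ligation is used to close the PDA, adverse events associated with the surgical ligation will not be reported". The section goes on to require follow-through on reported events ("Records relating to the subject's subsequent medical course must be maintained and submitted (as applicable) to the CCISC PDA Module PI") until the event subsides or stabilizes, and it requires all deaths to be reported.

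Elsewhere the protocol treats surgery as a possible consequence of a device complication:

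- Section 2.1 describes the outcomes of embolization as including "transcatheter retrieval at time of procedure or at a separate time, surgical retrieval", then organ damage and death.
- Appendix A makes a device- or procedure-related event a major complication if it results in, among other criteria, "A major open surgical intervention which is performed by a surgeon under general anesthesia".
- The adverse event form in Appendix D has an embolization outcome reading "Unsuccessful transcatheter retrieval, PDA surgically ligated" and, under other complications, a box labeled "Post PDA ligation syndrome".

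**The concern.** The note does not separate two different situations. In one, the attempt fails without incident and the infant later has a ligation, which is a different treatment with its own risks. In the other, the device embolizes or narrows a vessel, or the procedure injures something, and surgery follows because of that. In the second situation the harm of the operation is arguably part of the harm of the attempt, yet the same sentence tells sites not to report it.

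The study's aim is to describe safety in real-world use, and attempts that end in rescue surgery are among its most serious outcomes. A poorly chosen analysis population can be changed later. An event that a site was told not to report cannot be recovered by reanalysis.

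**Working it through.** No formula applies. The check sets the passages side by side.

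1. **Scope of the note.** It has two conditions: the procedure is abandoned, and ligation closes the PDA. It does not ask why the procedure was abandoned. It does not reach surgery performed after a device was left in place.

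2. **A worked case.** A device embolizes, cannot be retrieved by catheter, and is removed at an operation in which the PDA is ligated.

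| Item | Reportable? | Source |
|---|---|---|
| Embolization | Yes | 8.2 relatedness rule; Appendix D |
| Open surgery as its outcome | Yes; makes the event major | Appendix A; Appendix D outcome list |
| Course of the embolization | Yes, as applicable | 8.2 |
| Death | Yes | 6.1 and 8.2 |
| Bleeding, hemodynamic collapse or organ injury at the operation | Yes under the 8.2 relatedness rules if potentially related or of unknown relatedness; no under the 8.2 note if associated with the ligation | 8.2 against itself |

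Only the last row is in conflict.

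3. **Which instruction a site would follow.** The note is the more specific of the two. Appendix A's definition of a related event also requires that other interventions do not explain it, so a site can attribute a perioperative event to the surgery and treat the relatedness rules as not engaged. The rule on subsequent course follows the event already reported; it does not create a new report for a hemorrhage or organ injury at surgery.

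4. **Consequence for adjudication.** Section 6.4.2 has the CEC review the adverse events that section 5 makes reportable, together with deaths and other pre-defined events. A perioperative event that is not reported does not reach it. Section 4 follows infants who leave without a device for only 48 hours, so later follow-up is unlikely to fill the gap.

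5. **Effect on the primary safety rate.** Section 7.1 takes the number of subjects with an event over the section 7.4 population. Section 7.4 requires a device in the PDA on leaving the laboratory. An infant whose procedure was abandoned and who was then ligated contributes 0 to the numerator and 0 to the denominator, whatever is reported. The rate is unchanged.

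6. **Effect on section 7.5(d).** This summary of major and minor complications states no such exclusion, so these infants can appear in it.
   - In the embolization case the infant is already major, because Appendix A lists embolization needing open surgery. What is lost is the number and severity of events, not an affected subject.
   - If a device is withdrawn for vessel narrowing and the infant is then ligated, classification depends on whether the narrowing is held to have resulted in the open surgery. If so, the infant is again already major. If the ligation is held to have treated the PDA and not the narrowing, the narrowing could be classed as minor, and a life-threatening event at surgery would go unrecorded.
   - For scale only: if the listing used all 500 subjects, one reclassified infant would be 1/500 = 0.2 percentage points. The documents do not say how many there would be.

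7. **The form.** The embolization outcome that ends in ligation records an outcome, so it does not contradict the note. The ligation-syndrome box names a harm of ligation itself. After an abandoned procedure the form invites that entry and the note forbids it.

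**The case against.** The strongest reply is that keeping the harms of a different operation apart from those of the device is a defensible choice in a device registry, and that the note never says it applies when a complication forced the surgery. Both points are fair. The reach to bail-out surgery follows from the missing exception, not from an express statement. The reply justifies excluding events of a ligation after an uneventful failed attempt. It does not explain how the note fits with the two relatedness rules beside it when a complication came first.

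A reader might infer more than the text supports:

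- **That harm after failed attempts goes uncollected altogether.** It does not. The index complication, surgery as its outcome, events of unknown relatedness that a site does not tie to the ligation, the course of reported events and deaths all remain reportable.
- **That deaths would reach the CEC without context.** This is too strong. The CEC adjudicates deaths, and the Appendix G form asks for the cause. What may be missing is the perioperative detail.
- **That the primary safety rate is understated, by some amount to set against the 4.0 to 10.0% in section 7.1.** It is not, because section 7.4 removes these infants before the note has any effect. Such a figure would also need the share of attempts abandoned, the share ligated because of a complication, and the share with a major event not otherwise counted. The documents give none of these.

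It can also be said that the ligation-syndrome label is ambiguous and might mean instability after device closure. That is so, and it is why the form conflict is secondary and calls for a clearer label.

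**Conclusion.** The point holds as a conflict in the reporting rules with a limited effect. Followed literally, the note in section 8.2 removes from reporting the perioperative adverse events of a ligation that a device or procedure complication made necessary, while the same section requires potentially related events and events of unknown relatedness to be reported. The loss falls on the descriptive complication summary in section 7.5(d) and on the CEC's ability to judge severity and the relatedness of a later death. The primary safety rate as fixed by section 7.4 is unaffected, and no numerical magnitude can be supported.

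The conclusion assumes that an abandoned procedure leaves no device in the PDA and that sites apply the specific note over the general rules. It is worth correcting because the loss occurs at collection, but it does not undermine the main analysis.

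**What to change.** Three changes to the reporting text:

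- In section 8.2, limit the note to ligation that was not prompted by a device- or procedure-related adverse event.
- Add that when such an event led to the surgery, adverse events of that surgery are reported and sent to the CEC as consequences of the index attempt. State how this fits with the follow-up that section 4 gives to infants who leave without a device.
- Relabel the ligation-syndrome box in Appendix D to match, so that it is clear whether it covers instability after device closure, after ligation following a failed attempt, or both.

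The exclusion for ligation after an uneventful failed attempt stays. The cost is one or two sentences, one form label and a few extra adverse event forms. The descriptive complication listing may look somewhat less favorable. Clinical care and the primary safety analysis do not change.
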